5.0 RESEARCH PARTICIPANT SELECTION AND WITHDRAWAL

5.1 STUDY POPULATION

Twelve toddlers ages 18 months to <4 years (3 years 364 days) with a confirmed diagnosis of ASD.

5.2 INCLUSION CRITERIA

1. Age 18 months to <4 years (3 years 364 days) at the time of consent

- 2. Confirmed clinical DSM-5 diagnosis of Autism Spectrum Disorder using the DSM-5 Checklist as informed by the Brief Observation of Symptoms of Autism (BOSA) Assessment.
- 3. Fragile X testing performed and negative; constitutional microarray (CMA) and/or whole exome sequencing performed and results not linked to autism diagnosis
- 4. Stable on current psychoactive medication regimen (dose and dosing schedule) for at least 2 months prior to infusion of study product
- 5. Normal absolute lymphocyte count (≥1500/uL)
- 6. Participant and parent/guardian are English speaking
- 7. Able to travel to Duke University for two multi-day visits (baseline and six months) and parent/guardian is able to participate in interim surveys and interviews
- 8. Parental consent from at least one parent or guardian.

5.3 EXCLUSION CRITERIA

- 1. General:
 - a. Review of medical records indicates ASD diagnosis not likely
 - b. Screening data suggests that participant would not be able to comply with the requirements of the study procedures as assessed by the study team
 - c. Family is unwilling or unable to commit to participation in all study-related assessments, including protocol follow up
 - d. Sibling is enrolled in this (Duke TACT) study
- 2. Genetic:
 - Records indicate that child has a known genetic syndrome such as (but not limited to) Fragile X syndrome, neurofibromatosis, Rett syndrome, tuberous sclerosis, PTEN mutation, cystic fibrosis, muscular dystrophy or a genetic mutation known to be associated with ASD

- b. Known pathogenic mutation or copy number variation (CNV) associated with ASD (e.g., 16p11.2, 15q13.2, 2q13.3)
- 3. Infectious:
 - a. Known active CNS infection
 - b. Evidence of uncontrolled infection based on records or clinical assessment
 - c. Known HIV positivity
 - d. Exposure to COVID-19 in the preceding 14 days or positive COVID-19 test in the previous 28 days. Subjects with a past history of infection with COVID-19 must be symptom-free for 14 days prior to the initial visit

4. Medical:

- a. Known metabolic disorder
- b. Known mitochondrial dysfunction
- c. History of unstable epilepsy or uncontrolled seizure disorder, infantile spasms, Lennox Gastaut syndrome, Dravet syndrome, or other similar chronic seizure disorder
- d. Active malignancy or prior malignancy that was treated with chemotherapy
- e. History of a primary immunodeficiency disorder
- f. History of autoimmune cytopenias (i.e., ITP, AIHA)
- g. Coexisting medical condition that would place the child at increased risk for complications of study procedures
- h. Concurrent genetic or acquired disease or comorbidity(ies) that could require a future stem cell transplant
- i. Significant sensory (e.g., blindness, deafness, uncorrected hearing impairment) or motor (e.g., cerebral palsy) impairment
- j. Impaired renal or liver function as determined by serum creatinine >1.5mg/dL or total bilirubin >1.3mg/dL, except in patients with known Gilbert's disease
- k. Significant hematologic abnormalities defined as: Hemoglobin <10.0 g/dL, WBC < 3,000 cells/mL, ALC <1000/uL, Platelets <150 x 10e9/uL
- I. Known clinically relevant physical dysmorphology associated with neurodevelopmental conditions.
- 5. Current/Prior Therapy:
 - a. History of prior cell therapy
 - b. Current or prior use of IVIG or other anti-inflammatory medications with the exception of NSAIDs
 - c. Current or prior immunosuppressive therapy
 - i. No systemic steroid therapy that has lasted >5 days within 4 weeks prior to enrollment. Topical and inhaled steroids are permitted.

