Screening for the study is conducted under a separate, IRB-approved screening protocol (Pro00063563). Under this protocol, after written informed consent is obtained from a parent/guardian, the patient's medical and psychological records, therapy records, photographs, behavioral videos, and results of genetic testing are obtained and reviewed by two teams. The medical review is conducted by a team of pediatric nurses, nurse practitioners, and physicians to identify the presence of any metabolic, immunologic, neurologic, sensory, genetic, or laboratory exclusion criteria. If no exclusion criteria are identified, the psychiatric review is then conducted by a combination of psychologists, psychiatrists, and other clinically trained staff with expertise in diagnosing and treating children with ASD. They perform an extensive review of the patient's psychological records as well as any therapy records available. A patient must be approved by both medical and psychiatric screening teams to proceed with further laboratory, phone, teleconference, or in-person screening and study enrollment. Should a concern for a previously undiagnosed condition or genetic finding arise during the screening process, this will be discussed with the patient's parent(s)/guardian(s) and a referral will be made to an appropriate medical or psychiatric provider for evaluation and treatment, if indicated.

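### Exclusion 4k prints an impossible platelet limit and an ALC limit that does not match inclusion 5; exclusions 5b, 5c and 5c.i do not state one rule on steroid exposure

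*Combined protocol and SAP*

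**What the plan says.** Section 5.3, item 4k, sets the laboratory exclusions: "Significant hematologic abnormalities defined as: Hemoglobin <10.0 g/dL, WBC < 3,000 cells/mL, ALC <1000/uL, Platelets <150 x 10e9/uL". Section 5.2, item 5, sets a separate lymphocyte requirement: "Normal absolute lymphocyte count (≥1500/uL").

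Three items in section 5.3 bear on steroids:

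- 5b excludes "Current or prior use of IVIG or other anti-inflammatory medications with the exception of NSAIDs".
- 5c excludes "Current or prior immunosuppressive therapy".
- 5c.i, placed under 5c, reads "No systemic steroid therapy that has lasted >5 days within 4 weeks prior to enrollment" and adds "Topical and inhaled steroids are permitted".

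Section 5.4 gives the medical review team the task "to identify the presence of any metabolic, immunologic, neurologic, sensory, genetic, or laboratory exclusion criteria". It also says "Screening for the study is conducted under a separate, IRB-approved screening protocol (Pro00063563"). That screening protocol is not among the documents. The schedule in section 7.6.1 lists the blood count at screening but gives no limits, and no other section restates or corrects 4k.

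**The concern.** These are working eligibility rules, not background text. The review team has to apply them to each child. Section 12.5 treats enrolment against the eligibility criteria without the sponsor's prior approval as a protocol violation, and section 11.3 opens the records to audit and inspection.

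A limit that cannot be applied as printed forces staff to supply their own. Two ALC limits leave it unclear which was intended. Steroid items that can be read in different ways let two careful reviewers decide differently on the same child. What is at stake is whether the eligibility of the 12 planned children can be verified against the approved text.

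**Working it through.** The limits are printed, not derived, so there is no figure of the plan to reproduce. The check uses unit conversion (1 mL = 1,000 uL; 1 L = 10^6 uL; 1 uL = 10^9 fL), the fact that lymphocytes are part of the white cell count, and a side-by-side reading of the steroid items.

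**Platelets (4k).**

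- If 10e9 means 10^9, the limit is 150 x 10^9 = 1.5 x 10^11 per uL. That is 1.5 x 10^11 x 10^6 = 1.5 x 10^17 per L, or 10^6 times the same digits expressed per litre.
- Space per platelet is 10^9 fL / (1.5 x 10^11) = 0.0067 fL.
- In strict e-notation 10e9 is 10^10. The limit is then 1.5 x 10^12 per uL, with 0.00067 fL per platelet.
- The documents give no platelet volume. Assuming 2 to 15 fL, the first reading needs 1.5 x 10^11 x 2 / 10^9 = 300 uL to 1.5 x 10^11 x 15 / 10^9 = 2,250 uL of platelets in each uL of blood.

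Both readings are impossible, so every child's count lies below the printed limit.

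**ALC (4k against inclusion 5).**

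| ALC per uL | 4k | Inclusion 5 |
|---|---|---|
| below 1000 | excluded | not met |
| 1000 to 1499 | not excluded | not met |
| 1500 or more | not excluded | met |

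No child can have ALC below 1000 and at least 1500, so the 4k limit never changes a decision once inclusion 5 is applied. For ALC 1000 to 1499 the two items differ, and inclusion 5 decides.

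**Steroids (5b, 5c and 5c.i).** The middle column assumes that steroids count as anti-inflammatory (5b) or immunosuppressive (5c), and reads those items without the sub-item.

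| Exposure | 5b or 5c alone | 5c.i |
|---|---|---|
| Topical | excluded | permitted |
| Inhaled | excluded | permitted |
| Systemic, 5 days or less | excluded | not barred |
| Systemic, more than 5 days, over 4 weeks ago | excluded | not barred |
| Systemic, more than 5 days, within 4 weeks | excluded | excluded |

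The items disagree in 4 of 5 rows. Of those four exposures, the number excluded is 0 if 5c.i governs, 4 - 2 = 2 if only its express permission for topical and inhaled use overrides the broader items, and 4 if 5b or 5c stands alone. These are counts of exposure types, not of children.

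**WBC unit (item to check only).** As extracted, the limit is 3,000/mL = 3/uL. Inclusion 5 implies a white cell count of at least 1,500/uL, and 1,500 / 3 = 500, so a per-mL limit could exclude no one who meets inclusion 5. If per uL was meant (an assumption), the two versions differ only for counts from 1,500 to 2,999/uL.

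**The case against.** The strongest reply is that the platelet entry is an obvious slip, that no one would apply it literally, and that the screening protocol may carry the working limits. Much of this stands. A reader might infer that the trial as written can enrol none of its 12 children. That follows only from a literal reading that staff would not use. What remains is that the approved text contains no usable platelet limit, and the screening protocol is not available to show one. An extraction fault is an unlikely explanation, because uL came through correctly for ALC in the same line and in inclusion 5.

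On steroids, the reply is that 5c.i names them specifically and would be pointless if the broader items overrode it. That is the more natural reading. The conflict also depends on steroids falling under 5b or 5c, which the text does not state. But 5b gives NSAIDs as its only exception, 5c.i sits under 5c rather than 5b, and nothing says that it limits 5b.

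A reader might also infer that the WBC limit is wrong by a factor of 1,000. The documents as extracted cannot show this, because mL may be a misread unit. Nor do they support an inference of added infection risk: exclusion 3b (uncontrolled infection) and the postponement rule for illness in section 7.3 act independently of 4k.

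**Conclusion.** The point holds as a drafting error in operative criteria and is worth correcting. The platelet limit is unusable under either reading of 10e9. The ALC mismatch is also certain, but it changes no decision while inclusion 5 applies. The steroid conflict is conditional: it rests on steroids counting as anti-inflammatory or immunosuppressive, and it disappears if 5c.i is taken to govern, which is plausible but unstated. The WBC unit is unproven. How many children would be classified differently cannot be estimated from the documents. The consequence is that eligibility cannot be audited against the printed protocol.

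**What to change.** In section 5.3, restate the platelet limit in 4k in a unit that the laboratory reports. Reconcile the ALC limits in 4k and inclusion 5. Reconcile 5b, 5c and 5c.i so that one stated rule governs steroid exposure, for example through a cross-reference saying which item controls. Check the WBC unit against the source PDF and correct it only if mL is what is printed there. Confirm that screening protocol Pro00063563 uses the same limits and the same rule. Which limits and which rule are intended is for the sponsor to decide.

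The cost is a wording amendment to the eligibility criteria and one cross-check of the screening protocol. Assessments, sample size and analysis stay as they are.

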5.4 RESEARCH PARTICIPANT RECRUITMENT AND SCREENING

Patients may be recruited through IRB-approved advertising for the study on the websites of private CB banks, parent sponsored websites, the NMDP website, selected autism societies, local medical providers, or the Duke Center for Autism and Brain Development, through a record of inquiries for previous studies (brain injury database), and through the Duke Center for Autism and Brain Development research registry. Separate IRB approval will be obtained for any advertisements.

If a participant has consented to the Duke Center for Autism Research Repository (Pro00054178), study team members may access these data for purposes of screening, eligibility, or as source data in this study. Participants screened for or enrolled in the TACT study may also be approached per repository protocol to determine their interest in storing data from this study and

any future studies into the repository for future use. The consent form and participant-facing materials related to the Duke Center for Autism Research Repository are submitted and approved separately, through Pro00054178.

Screening for the study is conducted under a separate, IRB-approved screening protocol (Pro00063563). Under this protocol, after written informed consent is obtained from a parent/guardian, the patient's medical and psychological records, therapy records, photographs, behavioral videos, and results of genetic testing are obtained and reviewed by two teams. The medical review is conducted by a team of pediatric nurses, nurse practitioners, and physicians to identify the presence of any metabolic, immunologic, neurologic, sensory, genetic, or laboratory exclusion criteria. If no exclusion criteria are identified, the psychiatric review is then conducted by a combination of psychologists, psychiatrists, and other clinically trained staff with expertise in diagnosing and treating children with ASD. They perform an extensive review of the patient's psychological records as well as any therapy records available. A patient must be approved by both medical and psychiatric screening teams to proceed with further laboratory, phone, teleconference, or in-person screening and study enrollment. Should a concern for a previously undiagnosed condition or genetic finding arise during the screening process, this will be discussed with the patient's parent(s)/guardian(s) and a referral will be made to an appropriate medical or psychiatric provider for evaluation and treatment, if indicated.

5.5 EARLY WITHDRAWAL OF RESEARCH PARTICIPANTS

Criteria for Removal from Protocol Therapy:

- 1. Diagnosis of a genetic disease while under evaluation or on study.
- 2. Change in medical condition that precludes study participation.

Patients who are off protocol therapy are to be followed until they meet any one of the off-study criteria (see below). Follow-up data will be obtained on off-protocol participants unless consent is withdrawn. Participants that are taken off study prior to infusion of hCT-MSC will be considered not evaluable and can be replaced with another participant.

Off-Study Criteria:

- 1. Death.
- 2. Lost to follow-up.
- 3. Withdrawal of consent for any further data collection.
- 4. Completion of the final study visit.

6.0 STUDY PRODUCT

6.1 HUMAN UMBILICAL CORD TISSUE-DERIVED MESENCHYMAL STROMAL CELLS (hCT-MSC)

hCT-MSCs are a product of allogeneic cells manufactured from digested umbilical cord tissue that is expanded in culture, cryopreserved and banked. hCT-MSCs are manufactured from umbilical cord tissue donated to the Carolinas Cord Blood Bank, an FDA-licensed, FACT-accredited, public cord blood bank at Duke University Medical Center, after written informed consent from the baby's mother. Cord tissue is harvested from the placentas of male babies delivered by elective C-section after a normal, full-term pregnancy. Donor screening questionnaires are completed by the maternal donor, and maternal blood is tested for communicable diseases by the CLIA-certified donor screening laboratory. Donors must be eligible for donation to a public cord blood bank for allogeneic use. After delivery of the placenta and cord, the cord blood is aseptically drained from the placenta. Then the cord is dried and cleaned with chloropreps, separated from the base of the

placenta, placed in a sterile bottle containing Plasmalyte A, and transported to the Robertson CT2 GMP cell processing laboratory at room temperature in a validated container.

In the clean room manufacturing suite, in a biosafety cabinet, the cord tissue is removed from the media, placed in sterile dishes, cut into small pieces and then minced and digested in the Miltenyi Biotec GentleMacs Octo Dissociator with GMP-grade enzymes: hyaluronidase, DNase, collagenase, papain. The resultant cell suspension is placed in culture in Prime XV MSC Expansion XSFM (Irvine Scientific) media with 1% platelet lysate and grown to confluence (~7-14 days) to establish the P0 culture. To establish the master cell bank, P0 is harvested and cryopreserved in cryovials with Cryostor 10 media (BioLife), and stored in the vapor phase of liquid nitrogen. P1 and P2 cultures are grown under similar conditions, in hyperflasks or hyperstacks without platelet lysate, as needed to create the working cell bank and product for administration, respectively. Cells from P1 and P2 are removed from plastic cultureware using TrypLE (Gibco). The final product is derived from the P2 cultures which are harvested into plasmalyte with 5% human serum albumin, washed and cryopreserved in 5 compartment cryobags (Syngen) in 5 mL containing 50-100 million cells in a final concentration of 10% DMSO with dextran (Akron Scientific). On the day of administration, one compartment is thawed, diluted in 10-40 mls of plasmalyte IV solution, placed in a syringe or bag and transported to the bedside for administration over 30-60 minutes.

At each passage, the cell product is characterized by assessing cell surface phenotype by flow cytometry and functional assays via T-cell proliferation and organotypic models of microglial activation. Each lot, prior to cryopreservation of P2, will also be tested for sterility, endotoxin and mycoplasma and these tests must meet specifications. For dosing, release testing after thaw and dilution will include TNCC and viability via cellometer. Sterility cultures (14 day) are also initiated but results are not available at the time of infusion. See section 6.4 for management plan if sterility cultures subsequently turn positive post infusion. Patients will be dosed with 2x10⁶ hCT-MSCs/kg based on the post thaw count.

6.2 DONOR SCREENING AND TESTING

Donor screening and testing is performed per Carolinas Cord Blood Bank standard operating procedures to meet all requirements in 21CFR Part 1271. The screening and testing is current with recommendations and is approved by the FDA under biological license number 1870. Maternal donors of umbilical cord blood are screened and tested for HIV-1, HIV-2, hepatitis B virus (HBV, surface and core antigen), hepatitis C virus (HCV), Treponema pallidum (syphilis), CJD (screening only), Chagas, human T-lymphotropic virus types 1 and 2 (HTLV-1, HTLV-2) and CMV. Nucleic acid testing for HIV-1/2/O, HBV, WNV and HCV are also performed on maternal blood. Screening for Zika virus may also performed.

Because the cord tissue used for this study will be obtained from donors consented for cord blood donation to the Carolinas Cord Blood Bank, they will undergo donor screening and infectious disease testing per Carolinas Cord Blood Bank standard operating procedures. The cord blood-associated maternal samples and cord tissue MSC samples will be retained as reference samples for future testing as part of this study.

6.3 PROCESS AND FINAL FORMULATION

hCT-MSC is manufactured from a single umbilical cord tissue in a series of three steps that generate a master cell bank, a working cell bank, and the study product. The product for each step is frozen and stored in vapor phase in liquid nitrogen freezer. At P2, a representative cryobag

will be thawed and qualified prior to the treatment of any patients with that lot of product. Testing will include cell count, viability, phenotype, functional assays, endotoxin, mycoplasm, gram stain and sterility.

On the day of treatment, cells are thawed per SOP CT2-MSC-006, diluted in 10-40 mLs of plasmalyte-A + 5% HSA, and an aliquot removed for cell count, viability, and sterility culture. If the cells meet release criteria, the final product volume is adjusted to deliver the appropriate dose (2x10⁶ cells/kg) to the study participant. The cells are delivered to the bedside in a bag or syringe containing plasmalyte-A, 5% HSA, and residual DMSO. Any removed cell suspension is inoculated into aerobic and anaerobic culture bottles for sterility testing. The cells have a four-hour expiry post thaw.

The hCT-MSC final product will be released conditionally for administration to the patient after testing a post thaw cell count and viability. Final release will occur after the 14-day sterility culture period for the study product. In the event that a sterility culture turns positive after administration of the product, the organism will be identified and antibiotic sensitivities performed. The patient's family will be contacted to determine if they are symptomatic (ie fever). Asymptomatic patients will not be treated with antibiotics. Symptomatic patients will be evaluated and treated accordingly, with blood cultures and antibiotics as appropriate. All patients receiving a product with subsequent positive sterility test will be followed with close, regular contact by a study nurse for 14 days after the positive sterility test is noted.

6.4 PACKAGING OF STUDY PRODUCT

All umbilical cord tissues will be assigned an ISBT Demand 128 bar code label or unique identifier, which is carried through to all in-process and final hCT-MSC products. In addition, the CT2 GMP facility will provide a final product label for each hCT-MSC product. The product label will include a space to affix the bar code label as well as space for the participant number, date and time of product expiry, and any other pertinent information. As a participant is enrolled, a participant number will be assigned which will link to the 12 digit ISBT number bar code number assigned to the umbilical cord blood tissue. The final product will be assigned a lot number (manufacturing operation number) and expiry date and time that will be denoted on the Certificate of Analysis and product label. The participant number and ISBT bar code number of the product will be also listed on the Certificate of Analysis. All products will be transported from the CT2 laboratory to the infusion center in a validated cooler by courier.

6.5 ADMINISTRATION OF PRODUCT

Patients will be admitted to the infusion center on the day of their scheduled infusion. Patients may require some sedation prior to the IV placement if they are unable to remain still or cooperate. A peripheral IV will be placed by clinical or study staff. Patients will be premedicated with Benadryl 0.5mg/kg/dose IV and Solumedrol 0.5-1mg/kg IV. The hCT-MSCs or placebo product will be administered intravenously over 30-60 minutes. Vital signs (heart rate, blood pressure, temperature, respiratory rate) will be attempted upon arrival to the clinic and monitored as clinically indicated. Pulse oximetry will be monitored continuously throughout the infusion and for at least 5 minutes post infusion. Patients should be observed a minimum of 15-30 minutes post infusion.

